#### 8.4.1. PK Blood Sample Collection and Handling

Time points of PK blood sample collection are outlined in [Table 14](#)[Table 14](#) (BID dosing) and [Table 15](#)[Table 15](#) (QD dosing) for Dose Escalation and [Table 16](#)[Table 16](#) for Dose Expansion in Phase 1. Time points of PK blood sample collection for DDI sub-study and food effect sub-study are outlined in [Table 17](#)[Table 17](#), [Table 18](#)[Table 18](#) and [Table 19](#)[Table 19](#), respectively.

On PK sampling days, DS-1594b will be administered during the clinic visit as instructed by study personnel. Complete dosing and sampling information, including the exact dates and times of PK blood draw and exact dates and times of the last study drug dose prior to PK sampling and the study drug dose on the day of PK sampling (i.e. dose after pre-dose PK sampling), will be obtained on all PK sampling days and recorded on eCRF and on the CRO requisition form(s). If vomiting occurs within 4 hours of dose administration, the vomiting time should be documented on the eCRF. No re-dosing of the subject will be permitted during that period.

An unscheduled PK sample should be collected if a subject experiences an adverse event that results in an unscheduled visit or fits the criteria of a SAE, or if the triplicate ECG reading shows QTcF interval prolongation of  $> 60$  msec change from baseline or new absolute QTcF  $\geq 500$  msec.

Residual PK samples may also be used for exploratory analysis to further characterize the PK of DS-1594b and all of its metabolite(s). This may include using leftover samples for protein binding analysis or metabolite profiling (e.g. other metabolites and markers for metabolic enzyme activity such as 4-beta hydroxy cholesterol levels), if there is sufficient sample remaining.

For the food effect sub-study, meal records will be collected including the start and end time of the meal associated with each DS-1594b dose administered in the clinic on PK sampling days (Cycle 1 Day 1 and Cycle 1 Day 8). Compliance with prandial conditions for non-PK sampling days (fed or fasting conditions) will be confirmed by the study personnel during study visits.

For the DDI sub-study, the actual dose, starting date/time and stopping date/time for the anti-fungal agents (posaconazole or voriconazole) must be recorded on the eCRF. If vomiting of

these agents occurs within 5 hours of dose administration, the vomiting time should be documented on the eCRF.

All blood samples will be taken by either direct venipuncture or venous catheter or indwelling cannula inserted in a forearm vein. Instructions for the handling of blood samples and shipping of plasma PK samples are included in a separate document (eg, laboratory manual).

**Table 14: DS-1594b PK Blood Collection for Twice a Day (BID) Dosing During Phase 1 [Excluding Subjects Enrolled in DDI and Food Effect Sub-Studies] Dose Escalation**

Cycle	Day	Scheduled Time Point
1	1	Pre-dose/0h a
1	1	Post-dose 0.5h ( $\pm$ 5 min)
1	1	Post-dose 1h ( $\pm$ 10 min)
1	1	Post-dose 2h ( $\pm$ 10 min)
1	1	Post-dose 3h ( $\pm$ 10 min)
1	1	Post-dose 4h ( $\pm$ 10 min)
1	1	Post-dose 6h ( $\pm$ 10 min)
1	1	Post-dose 8h ( $\pm$ 10 min)
1	1	Post-dose 12h ( $\pm$ 60 min) (i.e. pre-dose of Cycle 1 Day 1 evening dose)
1	2	Pre-dose/0h a
1	5	Pre-dose/0h a
1	8	Pre-dose/0h a
1	8	Post-dose 0.5h ( $\pm$ 5 min)
1	8	Post-dose 1h ( $\pm$ 10 min)
1	8	Post-dose 2h ( $\pm$ 10 min)
1	8	Post-dose 3h ( $\pm$ 10 min)
1	8	Post-dose 4h ( $\pm$ 10 min)
1	8	Post-dose 6h ( $\pm$ 10 min)
1	8	Post-dose 8h ( $\pm$ 10 min)
1	8	Post-dose 12h ( $\pm$ 60 min) (i.e. pre-dose of Cycle 1 Day 8 evening dose)
1	15	Pre-dose/0h a
1	15	Post-dose 2h ( $\pm$ 10 min)
1	15	Post-dose 4h ( $\pm$ 10 min)
1	15	Post-dose 6h ( $\pm$ 10 min)
1	15	Post-dose 8h ( $\pm$ 10 min)
1	21	Pre-dose/0h a
1	21	Between 2-4 hours post-dose

Cycle	Day	Scheduled Time Point
2	1	Pre-dose/0h a
3	1	Pre-dose/0h a
4	1	Pre-dose/0h a
5	1	Pre-dose/0h a
6	1	Pre-dose/0h a
7	1	Pre-dose/0h a
8	1	Pre-dose/0h a
Unscheduled		Anytime
After intra-patient dose escalation (see Section 6.9):		
Cycle X of the new higher dose level or different dosing regimen (frequency)	8	Pre-dose/0h a
Cycle X of the new higher dose level or different dosing regimen (frequency)	8	Between 2-4 hours post-dose
Unscheduled		Anytime

All measurement times are relative to dose of DS-1594b unless otherwise specified

a PK sample should be taken immediately prior to the next administration of DS-1594b

**Table 15: DS-1594b PK Blood Collection for Daily (QD) Dosing During Phase 1 [Excluding Subjects Enrolled in DDI and Food Effect Sub-Studies] Dose Escalation**

Cycle	Day	Scheduled Time Point
1	1	Pre-dose/0h a
1	1	Post-dose 0.5h ( $\pm$ 5 min)
1	1	Post-dose 1h ( $\pm$ 10 min)
1	1	Post-dose 2h ( $\pm$ 10 min)
1	1	Post-dose 3h ( $\pm$ 10 min)
1	1	Post-dose 4h ( $\pm$ 10 min)
1	1	Post-dose 6h ( $\pm$ 10 min)
1	1	Post-dose 8h ( $\pm$ 10 min)
1	2	Pre-dose/0h b
1	5	Pre-dose/0h a
1	8	Pre-dose/0h a
1	8	Post-dose 0.5h ( $\pm$ 5 min)
1	8	Post-dose 1h ( $\pm$ 10 min)
1	8	Post-dose 2h ( $\pm$ 10 min)
1	8	Post-dose 3h ( $\pm$ 10 min)
1	8	Post-dose 4h ( $\pm$ 10 min)

Cycle	Day	Scheduled Time Point
1	8	Post-dose 6h ( $\pm$ 10 min)
1	8	Post-dose 8h ( $\pm$ 10 min)
1	9	Pre-dose/0h c
1	15	Pre-dose/0h a
1	15	Post-dose 2h ( $\pm$ 10 min)
1	15	Post-dose 4h ( $\pm$ 10 min)
1	15	Post-dose 6h ( $\pm$ 10 min)
1	15	Post-dose 8h ( $\pm$ 10 min)
1	16	Pre-dose/0h d
1	21	Pre-dose/0h a
1	21	Between 2-4 hours post-dose
2	1	Pre-dose/0h a
3	1	Pre-dose/0h a
4	1	Pre-dose/0h a
5	1	Pre-dose/0h a
6	1	Pre-dose/0h a
7	1	Pre-dose/0h a
8	1	Pre-dose/0h a
Unscheduled		Anytime
After intra-patient dose escalation (see Section 6.9):		
Cycle X of the new higher dose level or different dosing regimen (frequency)	8	Pre-dose/0h a
Cycle X of the new higher dose level or different dosing regimen (frequency)	8	Between 2-4 hours post-dose
Unscheduled		Anytime

All measurement times are relative to dose of DS-1594b unless otherwise specified.

a PK sample should be taken immediately prior to the next administration of DS-1594b.

b Predose C1D2 PK sample is the same as 24 hours ( $\pm$  2h) C1D1 post-dose PK sample; it will be collected immediately prior the administration of DS-1594b.

c Predose C1D9 PK sample is the same as 24 hours ( $\pm$  2h) C1D8 post-dose PK sample; it will be collected immediately prior the administration of DS-1594b.

d Predose C1D16 PK sample is the same as 24 hours ( $\pm$  2h) C1D15 post-dose PK sample; it will be collected immediately prior the administration of DS-1594b.

**Table 16: DS-1594b PK Blood Collection During Phase 2 Dose Expansion**

Cycle	Day	Scheduled Time Point	Comment
1	1	Pre-dose/0h a	
1	1	Post-dose 0.5h ( $\pm$ 5 min)	Optional pending Phase 1 data
1	1	Post-dose 1h ( $\pm$ 10 min)	
1	1	Post-dose 2h ( $\pm$ 10 min)	
1	1	Post-dose 4h ( $\pm$ 10 min)	
1	1	Post-dose 6h ( $\pm$ 10 min)	
1	1	Post-dose 8h ( $\pm$ 10 min)	
1	2	Pre-dose/0h b	For daily (QD) dosing only
1	8	Pre-dose/0h a	
1	8	Post-dose 0.5h ( $\pm$ 5 min)	Optional pending Phase 1 data
1	8	Post-dose 1h ( $\pm$ 10 min)	
1	8	Post-dose 2h ( $\pm$ 10 min)	
1	8	Post-dose 4h ( $\pm$ 10 min)	
1	8	Post-dose 6h ( $\pm$ 10 min)	
1	8	Post-dose 8h ( $\pm$ 10 min)	
1	9	Pre-dose/0h c	For daily (QD) dosing only
1	15	Pre-dose/0h a	
1	15	Between 2-4 hours post-dose	
2	1	Pre-dose/0h a	
3	1	Pre-dose/0h a	
4	1	Pre-dose/0h a	
5	1	Pre-dose/0h a	
6	1	Pre-dose/0h a	
Unscheduled		Anytime	

All measurement times are relative to dose of DS-1594b unless otherwise specified

a PK sample should be taken immediately prior to the next administration of DS-1594b

b Predose C1D2 PK sample is the same as 24 hours ( $\pm$  2h) C1D1 post-dose PK sample; it will be collected immediately prior the administration of DS-1594b

c Predose C1D9 PK sample is the same as 24 hours ( $\pm$  2h) C1D8 post-dose PK sample; it will be collected immediately prior the administration of DS-1594b

**Table 17: DS-1594b PK Blood Collection for DDI Sub-Study with Antifungal Agents During Phase 1 After MTD Determination (N ~ 12)**

Cycle	Day	Scheduled Time Point	Comment
1	1	Pre-dose/0h a	
1	1	Post-dose 1h ( $\pm$ 10 min)	
1	1	Post-dose 2h ( $\pm$ 10 min)	

Cycle	Day	Scheduled Time Point	Comment
1	1	Post-dose 4h ( $\pm$ 10 min)	
1	1	Post-dose 6h ( $\pm$ 10 min)	
1	1	Post-dose 8h ( $\pm$ 10 min)	
1	8	Pre-dose/0h a	
1	8	Post-dose 0.5h ( $\pm$ 5 min)	
1	8	Post-dose 1h ( $\pm$ 10 min)	
1	8	Post-dose 2h ( $\pm$ 10 min)	
1	8	Post-dose 3h ( $\pm$ 10 min)	
1	8	Post-dose 4h ( $\pm$ 10 min)	Full PK profile in the absence of antifungal agents
1	8	Post-dose 6h ( $\pm$ 10 min)	
1	8	Post-dose 8h ( $\pm$ 10 min)	
1	8	Post-dose 12h ( $\pm$ 60 min) (i.e. pre-dose of Cycle 1 Day 8 evening dose) [for BID dosing only]	
1	9	Pre-dose/0h b [for daily dosing only]	
1	18	Pre-dose/0h a	
1	18	Post-dose 0.5h ( $\pm$ 5 min)	
1	18	Post-dose 1h ( $\pm$ 10 min)	
1	18	Post-dose 2h ( $\pm$ 10 min)	
1	18	Post-dose 3h ( $\pm$ 10 min)	
1	18	Post-dose 4h ( $\pm$ 10 min)	Full PK profile in the presence of antifungal agents
1	18	Post-dose 6h ( $\pm$ 10 min)	
1	18	Post-dose 8h ( $\pm$ 10 min)	
1	18	Post-dose 12h ( $\pm$ 60 min) (i.e. pre-dose of Cycle 1 Day 18 evening dose) [for BID dosing only]	
1	19	Pre-dose/0h c [for daily dosing only]	
2	1	Pre-dose/0h a	
3	1	Pre-dose/0h a	
4	1	Pre-dose/0h a	
Unscheduled		Anytime	

All measurement times are relative to dose of DS-1594b unless otherwise specified

a PK sample should be taken immediately prior to the next administration of DS-1594b

b Predose C1D9 PK sample is the same as 24 hours ( $\pm$  2h) C1D8 post-dose PK sample; it will be collected immediately prior the administration of DS-1594b

c Predose C1D19 PK sample is the same as 24 hours ( $\pm$  2h) C1D18 post-dose PK sample; it will be collected immediately prior the administration of DS-1594b

**Table 18: DS-1594b PK Blood Collection for DDI Sub-Study with Antifungal Agents During Phase 1 Before MTD Determination**

Cycle	Day	Scheduled Time Point	Comment
1	1	Pre-dose/0h a	
1	1	Post-dose 0.5h (± 5 min)	
1	1	Post-dose 1h (± 10 min)	
1	1	Post-dose 2h (± 10 min)	
1	1	Post-dose 3h (± 10 min)	
1	1	Post-dose 4h (± 10 min)	
1	1	Post-dose 6h (± 10 min)	
1	1	Post-dose 8h (± 10 min)	
1	1	Post-dose 12h (± 60 min) (i.e. pre-dose of Cycle 1 Day 1 evening dose) [for BID dosing only]	
1	2	Pre-dose/0h a	
1	5	Pre-dose/0h a	
1	8	Pre-dose/0h a	Full PK profile in the absence of antifungal agents
1	8	Post-dose 0.5h (± 5 min)	
1	8	Post-dose 1h (± 10 min)	
1	8	Post-dose 2h (± 10 min)	
1	8	Post-dose 3h (± 10 min)	
1	8	Post-dose 4h (± 10 min)	
1	8	Post-dose 6h (± 10 min)	
1	8	Post-dose 8h (± 10 min)	
1	8	Post-dose 12h (± 60 min) (i.e. pre-dose of Cycle 1 Day 8 evening dose) [for BID dosing only]	
1	9	Pre-dose/0h b [for daily dosing only]	
2	10	Pre-dose/0h a	Full PK profile in the presence of antifungal agents
2	10	Post-dose 0.5h (± 5 min)	
2	10	Post-dose 1h (± 10 min)	
2	10	Post-dose 2h (± 10 min)	
2	10	Post-dose 3h (± 10 min)	
2	10	Post-dose 4h (± 10 min)	
2	10	Post-dose 6h (± 10 min)	
2	10	Post-dose 8h (± 10 min)	
2	10	Post-dose 12h (± 60 min) (i.e. pre-dose of Cycle 2 Day 10 evening dose) [for BID dosing only]	
2	11	Pre-dose/0h c [for daily dosing only]	

Cycle	Day	Scheduled Time Point	Comment
3	1	Pre-dose/0h a	
4	1	Pre-dose/0h a	
5	1	Pre-dose/0h a	
6	1	Pre-dose/0h a	
Unscheduled		Anytime	

All measurement times are relative to dose of DS-1594b unless otherwise specified

a PK sample should be taken immediately prior to the next administration of DS-1594b

b Predose C1D9 PK sample is the same as 24 hours ( $\pm$  2h) C1D8 post-dose PK sample; it will be collected immediately prior the administration of DS-1594b

c Predose C2D11 PK sample is the same as 24 hours ( $\pm$  2h) C2D10 post-dose PK sample; it will be collected immediately prior the administration of DS-1594b

**Table 19: DS-1594b PK Blood Collection for Food Effect Sub-Study During Phase 1 After MTD Determination (N ~ 6)**

Cycle	Day	Scheduled Time Point	Comment
1	1	Pre-dose/0h a	
1	1	Post-dose 1h ( $\pm$ 10 min)	
1	1	Post-dose 2h ( $\pm$ 10 min)	
1	1	Post-dose 4h ( $\pm$ 10 min)	
1	1	Post-dose 6h ( $\pm$ 10 min)	
1	1	Post-dose 8h ( $\pm$ 10 min)	
1	8	Pre-dose/0h a	Full PK profile under fed condition with standard breakfast
1	8	Post-dose 0.5h ( $\pm$ 5 min)	
1	8	Post-dose 1h ( $\pm$ 10 min)	
1	8	Post-dose 2h ( $\pm$ 10 min)	
1	8	Post-dose 3h ( $\pm$ 10 min)	
1	8	Post-dose 4h ( $\pm$ 10 min)	
1	8	Post-dose 6h ( $\pm$ 10 min)	
1	8	Post-dose 8h ( $\pm$ 10 min)	
1	8	Post-dose 12h ( $\pm$ 60 min) (i.e. pre-dose of Cycle 1 Day 8 evening dose) [for BID dosing only]	
1	9	Pre-dose/0h b [for daily dosing only]	
1	18	Pre-dose/0h a	Full PK profile under fasting condition
1	18	Post-dose 0.5h ( $\pm$ 5 min)	
1	18	Post-dose 1h ( $\pm$ 10 min)	
1	18	Post-dose 2h ( $\pm$ 10 min)	
1	18	Post-dose 3h ( $\pm$ 10 min)	

Cycle	Day	Scheduled Time Point	Comment
1	18	Post-dose 4h ( $\pm$ 10 min)	
1	18	Post-dose 6h ( $\pm$ 10 min)	
1	18	Post-dose 8h ( $\pm$ 10 min)	
1	18	Post-dose 12h ( $\pm$ 60 min) (i.e. pre-dose of Cycle 1 Day 18 evening dose) [for BID dosing only]	
1	19	Pre-dose/0h c [for daily dosing only]	
2	1	Pre-dose/0h a	
3	1	Pre-dose/0h a	
4	1	Pre-dose/0h a	
Unscheduled		Anytime	

All measurement times are relative to dose of DS-1594b unless otherwise specified

a PK sample should be taken immediately prior to the next administration of DS-1594b

b Predose C1D9 PK sample is the same as 24 hours ( $\pm$  2h) C1D8 post-dose PK sample; it will be collected immediately prior the administration of DS-1594b

c Predose C1D19 PK sample is the same as 24 hours ( $\pm$  2h) C1D18 post-dose PK sample; it will be collected immediately prior the administration of DS-1594b

#### 8.4.2. Analytical Methods

Plasma DS-1594b and metabolites (if appropriate) will be measured at a laboratory designated by Daiichi Sankyo using a validated LC/MS assay.

#### 8.5. Cardiac Assessment (Electrocardiograms)

A standard 12-lead ECG or Holter monitor will be used to collect the ECG timepoints described in [Table 20](#) and [Table 21](#) of Phase 1 and Phase 2, respectively. At all scheduled timepoints, ECGs must be performed in triplicate. The triplicate ECGs must be taken approximately  $\geq$ 1 minute apart, with the subject in the supine/semi-recumbent position. All ECGs recorded for each time point must be transmitted electronically to a central laboratory and must be centrally reviewed by an independent reviewer. Any original ECG not transmitted electronically to the central laboratory must be forwarded for central review. **All ECGs must be performed within 15 mins prior to the collection of all PK samples.**

Formatted: C-Hyperlink

Formatted: C-Hyperlink

The ECG collection plan is described in [Table 20](#) and [Table 21](#), respectively, for Phase 1 Dose Escalation and Phase 1 Dose Expansion / Phase 2.

Formatted: C-Hyperlink

Formatted: C-Hyperlink

**Table 20: ECG Collection During Phase 1 Escalation**

Cycle	Day	Time	Comment
Screening	-28 to -1	Anytime	
1	1	Pre-dose/0h a	
1	1	Post-dose 2h	
1	1	Post-dose 4h	
1	1	Post-dose 6h	
1	1	Post-dose 8h	

1	1	Post-dose 12h b (or Cycle 1 Day 1 pre-evening dose)	
1	2	Pre-dose/0h a (Post-dose 12h from evening dose on Cycle 1, Day 1 [if BID dosing], or post-dose 24h from morning dose on Cycle 1, Day 1 [if QD dosing])	
1	5	Pre-dose/0h a	
1	8	Pre-dose/0h a	
1	8	Post-dose 2h	
1	8	Post-dose 4h	
1	8	Post-dose 6h	
1	8	Post-dose 8h	
1	8	Post-dose 12h b (or Cycle 1 Day 8 pre-evening dose)	For BID dosing only
1	9	Pre-dose/0h a (same as post-dose 24 h of C1D8)	For daily (QD) dosing only
1	15	Pre-dose/0h a	
1	15	Post-dose 2h	
1	15	Post-dose 4h	
1	18	Pre-dose/0h a	DDI sub-study only d
1	18	Post-dose 2h	DDI sub-study only d
1	18	Post-dose 4h	DDI sub-study only d
1	18	Post-dose 6h	DDI sub-study only d
1	18	Post-dose 8h	DDI sub-study only d
1	18	Post-dose 12h b (or Cycle 1 Day 18 pre-evening dose)	DDI sub-study only d For BID dosing only
1	19	Pre-dose/0h a (same as post-dose 24 h of C1D18)	DDI sub-study only d For QD dosing only
1	21	Pre-dose/0h a	
1	21	Between 2-4 hours post-dose	
2	1	Pre-dose/0h a	
2	10	Pre-dose/0h a	DDI sub-study only c
2	10	Post-dose 2h	DDI sub-study only c
2	10	Post-dose 4h	DDI sub-study only c
2	10	Post-dose 6h	DDI sub-study only c
2	10	Post-dose 8h	DDI sub-study only c
2	10	Post-dose 12h b (or Cycle 2 Day 10 pre-evening dose)	DDI sub-study only c For BID dosing only
2	11	Pre-dose/0h a (same as post-dose 24 h of C2D10)	DDI sub-study only c For QD dosing only
3-8	1	Pre-dose/0h a	
During treatment after Cycle 6	Any day c	Anytime	

**After intra-patient dose escalation (see Section 6.9):**

Cycle X of the new higher dose level	8	Pre-dose/0h a	
Cycle X of the new higher dose level	8	Between 2-4 hours post-dose	

End of Treatment	--	--	
------------------	----	----	--

All measurement times are relative to dose of DS-1594b unless otherwise specified

a Pre-dose assessment should be taken prior to the next administration of DS-1594b and within 15 mins prior to PK collection

b 12-hour assessment must be performed prior to the next dose and within 15 mins prior to PK collection

c ECG should be performed only if clinically indicated

d For subjects participating in the DDI sub-study AFTER MTD declaration (N ~ 12), additional triplicate ECGs will be performed on Cycle 1 Day 18 and Day 19 to coincide with PK assessments in which DS-1594b is co-administered with antifungal agents (posaconazole, voriconazole) that are potent CYP3A inhibitors

e For subjects participating in the DDI sub-study BEFORE MTD declaration, additional triplicate ECGs will be performed on Cycle 2 Day 10 and Day 11 to coincide with PK assessments in which DS-1594b is co-administered with antifungal agents (posaconazole) that are potent CYP3A inhibitors

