### 3.1. Rationale for dose and regimen selection

The selection of the starting dose level and regimen is based on the extrapolation of data from cell line efficacy models and toxicology studies in rodents and monkeys.

The DS-1594b Severely Toxic Dose in 10% of animals (STD10) in mice was greater than 300 mg/kg/day and the Highest Non-Severely Toxic Dose (HNSTD) in monkeys was 60 mg/kg/day. The human equivalent dose (HED) of 300 mg/kg/day in mice, based on allometric scaling by body surface area, is approximately 24.3 mg/kg, and using 1/10th of the HED gives a dose of 2.4 mg/kg as the recommended starting human dose for the proposed clinical study. The value of 2.4 mg/kg is lower than a starting dose (3.2 mg/kg) derived from 1/6th of the HED for the HNSTD (60 mg/kg/day) in monkeys. The estimated human systemic exposure at the starting dose exceeds the IC50 of DS-1594b against MV-4-11 human AML cell line (1.97 nM [1.13 ng/mL]), and inhibition of cell proliferation is expected. Therefore, the value of 2.4 mg/kg is considered the appropriate starting dose for the proposed clinical study. No supportive data are available at this stage that would suggest body size-based dosing would reduce human inter-subject variability in PK. Thus, based on an average body weight of 60 kg human, the recommended starting human dose is 140 mg/day. A dosing approach with 70 mg given twice a day will be adopted in order to reduce Cmax while maintaining AUC compared to once-daily dosing to mitigate potential QT interval prolongation risk, given the observed QTc interval prolongation signal seen in monkeys (see Section 2.4.2). In addition, the estimated clinical half-life of DS-1594b is ~ 7 to 8 hours, which also supports a twice daily dosing regimen.

Based on emerging clinical data to assess the PK and safety profile of DS-1594b, the frequency of dosing may be adjusted to once daily (QD), if deemed appropriate and supported by safety data. In this case, dose escalation would follow the same rules as the BID schedule. The SRC

may recommend the enrollment of simultaneous QD and BID dosing regimens or may switch from BID dosing to QD dosing.

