## 6.9. Intra-Patient Dose Escalation (IPDE)

Intra-patient dose escalation (IPDE) of DS-1594b is permitted for subjects enrolled in the dose escalation portion of the study who may benefit from IPDE after approval from the PI or Co-PI, provided the subject meets all of the following criteria:

- The subject has failed to achieve a complete remission (CR) or has experienced disease progression on treatment with DS-1594b,
- The subject has not experienced a DLT or treatment related adverse event requiring DS-1594b dose reduction or interruption.

The dose may be escalated up to a dose level that has previously been established to be safe and tolerable in at least 3 DLT evaluable subjects (for example, a subject enrolled at 50mg BID may be dose escalated to 70mg BID only after the 70mg BID dose level has been declared safe and tolerable in at least 3 DLT evaluable subjects).

Additionally, a subject may be switched to an alternative DS-1594b dosing regimen (BID vs. QD) once they have completed the DLT evaluation period in Phase I, if that dosing regimen has been found to be safe and tolerable in at least 3 DLT evaluable subjects (for example, from 50 mg BID to 100 mg QD).

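### After a frequency-only BID/QD switch in Phase 1, Tables 14 and 15 schedule a 2-4 h PK sample but Table 20 schedules no matching ECG

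*Combined protocol and SAP*

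**What the plan says.** Section 6.9, on intra-patient dose escalation (IPDE), also covers regimen changes: "a subject may be switched to an alternative DS-1594b dosing regimen (BID vs. QD) once they have completed the DLT evaluation period". The target regimen must already have been found safe and tolerable in at least 3 DLT-evaluable subjects. The example is "from 50 mg BID to 100 mg QD", which leaves the daily dose at 100 mg.

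Three tables carry a block for the period after IPDE, and each refers to Section 6.9. In Tables 14 and 15 (PK), the Day 8 pre-dose and 2-4 h samples apply to "Cycle X of the new higher dose level or different dosing regimen (frequency"). In Table 20 (ECG), the Day 8 pre-dose and 2-4 h rows apply to "Cycle X of the new higher dose level", and frequency is not mentioned.

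Section 3.1 explains that twice-daily dosing was adopted to reduce Cmax at the same AUC "compared to once-daily dosing to mitigate potential QT interval prolongation risk". Section 9.4.10 plans to plot QTc change from baseline against the time-matched DS-1594b concentration.

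**The concern.** The PK tables treat a change of frequency as a trigger separate from a dose-level increase. The ECG table keeps only the second trigger. A subject who moves from twice-daily to once-daily dosing at the same daily dose therefore meets the PK trigger but not the ECG trigger.

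Two things are at stake. The first is monitoring. QTc prolongation is an adverse event of special interest, and the plan's own reason for twice-daily dosing was to hold down Cmax. A switch to once-daily dosing is thus a change after which a post-dose ECG is informative. The QTcF actions in Table 12 and the QTcF-triggered unscheduled PK sample in Section 8.4.1 can operate only if an ECG is recorded. The second is analysis. The 2-4 h sample drawn after the switch has no scheduled ECG to pair with for Section 9.4.10.

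**Working it through.** The plan states no figure to reproduce. The check is a comparison of the schedules, followed by an illustrative calculation.

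**Step 1. Schedules after IPDE**

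| | Tables 14 and 15 (PK) | Table 20 (ECG) |
|---|---|---|
| Source cited | Section 6.9 | Section 6.9 |
| Day and times | Day 8, pre-dose and 2-4 h | Day 8, pre-dose and 2-4 h |
| Dose-level increase | yes | yes |
| Change of frequency alone | yes | not named |

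**Step 2. Other ECGs in Table 20 from Cycle 2 on, outside the DDI sub-study**

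- Day 1 of Cycle 2 and Day 1 of Cycles 3-8: 1 + 6 = 7 time points, all pre-dose.
- After Cycle 6, on any day: "ECG should be performed only if clinically indicated".
- End of Treatment: one ECG with no time relative to dose.
- Reactive ECGs after QTcF above 480 ms (Section 6.2.3.1). These require a prolongation to have been seen first.

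Table 32 adds no ECG for IPDE and refers to Table 20 for timing. A frequency-only switch therefore has 1 scheduled post-dose PK sample and 0 scheduled post-dose ECGs.

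**Step 3. Could other text supply the missing ECG?**

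- Section 5.1.2, item 6, places the morning dose on PK days after the pre-dose ECG and the blood draw. The post-switch Day 8 is a PK day, so a pre-dose ECG is arguably implied. A 2-4 h ECG is not.
- Section 8.5 requires ECGs within the 15 minutes before PK collection. If this created an ECG for every PK sample, there would be ECGs at 0.5, 1 and 3 h, where Tables 14 and 15 draw PK and Table 20 lists none. The sentence fits better as a rule on when a listed ECG is taken.

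The firm gap is the 2-4 h ECG.

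**Step 4. Illustration of exposure at equal daily dose**

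Input from the plan: estimated half-life 7-8 h (Section 3.1). Assumptions not in the plan: linear one-compartment kinetics, steady state, and first-order absorption with ka of 0.3 to 2 per hour, or bolus as the limit. Let k = ln 2 / half-life, and compare a dose 2D every 24 h with D every 12 h.

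- Bolus peak ratio = 2 / (1 + e^(-12k)).
- Bolus trough ratio = 2e^(-12k) / (1 + e^(-12k)).
- Half-life 7 h: e^(-12k) = 0.305. Peak ratio 2 / 1.305 = 1.53; trough ratio 0.610 / 1.305 = 0.47.
- Half-life 8 h: e^(-12k) = 0.354. Peak ratio 2 / 1.354 = 1.48; trough ratio 0.707 / 1.354 = 0.52.

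With absorption, the steady-state concentration at time t for dose X and interval τ is proportional to X·ka/(ka − k) · [e^(-kt)/(1 − e^(-kτ)) − e^(-ka·t)/(1 − e^(-ka·τ))]. Results for once-daily relative to twice-daily dosing:

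| Half-life | ka (per h) | Peak ratio | Trough ratio | Once-daily time to peak (h) |
|---|---|---|---|---|
| 7 h | 0.3 | 1.36 | 0.50 | 5.0 |
| 7 h | 2 | 1.51 | 0.47 | 1.5 |
| 8 h | 0.3 | 1.32 | 0.55 | 5.2 |
| 8 h | 2 | 1.46 | 0.52 | 1.6 |

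Over the whole range the peak ratio is 1.32 to 1.53 and the trough ratio 0.47 to 0.55. The modelled time to peak runs from about 1.5 to 5.2 h, so a 2-4 h sample is a post-dose sample and not necessarily the peak.

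**The case against.** The strongest reply is that the gap is small and probably unintended. Table 20 cites Section 6.9, which contains the switch provision, so the authors may have meant to include it. A switch is allowed only to a regimen already found safe and tolerable in at least 3 DLT-evaluable subjects. Subjects enrolled directly on once-daily dosing have triplicate post-dose ECGs in Cycle 1 on Days 1, 8, 15 and 21. Post-dose QTc on that regimen is therefore seen in other subjects before anyone switches. The gap also closes if the switch is at the same time a dose-level increase, and it never arises if once-daily dosing is not opened. All of this stands and limits the point to follow-up of the individual switched subject. It does not remove the point: Section 6.9 sets the same precondition for dose escalation, and Table 20 still schedules a 2-4 h ECG there.

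A reader might infer more than the documents support in four ways:

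- That the protocol says a switch raises QT risk. Section 3.1 says only that twice-daily dosing was chosen to reduce Cmax and mitigate a potential risk; the rest is inference. Switches may also go from once-daily to twice-daily, where a lower Cmax would be expected.
- That no ECG at all belongs to the Day 8 visit. Section 5.1.2, item 6, arguably implies the pre-dose one.
- That the peak rises by 50%. That is the top of a range resting on assumed linear kinetics and absorption. Section 2.4.2 reports CYP3A4 metabolism and time-dependent CYP3A inhibition, so linearity is uncertain. An assumed longer half-life shrinks the bolus ratio: 2 / 1.5 = 1.33 at 12 h and 2 / 1.595 = 1.25 at 16 h.
- That a planned within-subject comparison of regimens is lost. Section 9.4.10 plans none; its mixed model is optional, and Cycle 1 still supplies post-dose pairs from each regimen used.

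**Conclusion.** The ECG and PK schedules after IPDE do not agree, and they must be reconciled. As written, a BID/QD switch without a dose-level increase has a 2-4 h PK sample and no scheduled time-matched ECG. Outside the DDI sub-study, all later dose-timed ECGs are pre-dose. In the direction from twice-daily to once-daily, and under the assumptions stated in the working, those pre-dose ECGs would be taken at about half the former trough concentration while the peak is about 1.3 to 1.5 times as high. The mismatch itself rests on the table wording alone and needs no kinetic assumption; the ratios are illustrative. The effect is confined to individual QT monitoring and to one missing concentration-QTc pair per switched subject. The primary endpoints, sample size and error rates are untouched.

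**What to change.** Reconcile the trigger of the two post-IPDE rows in Table 20 with Tables 14 and 15, so that a change of dosing frequency is covered as well as a dose-level increase. The Day 8 pre-dose and 2-4 h ECGs would then each precede a PK sample that is already scheduled, within the 15 minutes set in Section 8.5, and the 2-4 h sample would have its pair for Section 9.4.10. If frequency changes were left out of Table 20 on purpose, the protocol should say so and give the reason.

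The cost is a wording change in two rows and up to two triplicate ECG time points, for switched subjects only, on a day when they are already dosed and sampled at site. If Section 5.1.2, item 6, is taken to require the pre-dose ECG already, the addition is one time point.
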